---

## LIST OF ABBREVIATIONS

---

Abbreviation	Definition
--------------	------------

(e)CRF	(electronic) Case Report Form
CI	Coordinating Investigator
DPA	Data Processing Annex
DTA	Data Transfer Agreement
EC	Ethics Committee
EU	European Union
GCP	Good Clinical Practice (latest version of ICH E6)
GDPR	General Data Protection Regulation
ICH	International Conference on Harmonisation
JCI	Joint Commission International
PI	Principal Investigator (Participating Site)
SOP	Standard Operating Procedure
BBG	Brilliant Blue G
BCVA	Best Corrected Visual Acuity
DC	Declaration of Conformity
ERM	Epiretinal Membrane(s)
ICG	Indocyanine Green
IFU	Instruction For Use
ILM	Inner Limiting Membrane
KWS	Klinisch Werkstation (EMR used in UZLeuven)
PEG	Poly-Ethylene Glycol
PBS	Phosphate Buffer Saline
PVR	Proliferative vitreoretinopathy
RPE	Retinal Pigment Epithelial cells
TB	Trypan Blue
EMR	Electronical Medical Record
MDR	Medical Device Regulation
NA	Not applicable

## FUNDING AND SUPPORT

Funder	Type of Financial or Non-Financial Support
Arcad/BVI	grant

## ROLES AND RESPONSIBILITIES

The Principle Investigator (PI) is responsible for the conduct of the Study at his/her Participating Site, and for protecting the rights, safety and well-being of Study participants. As such the PI must ensure adequate supervision of the Study conduct at the Participating Site. If any tasks are delegated, the PI will maintain a log of appropriately qualified persons to whom he/she has delegated specified Study-related duties. The PI will ensure that adequate training is provided and documented for all Study staff, prior to conducting assigned Study-related activities. Even when certain activities are delegated, the PI will ultimately remain responsible for the conduct of the Study at his/her Participating Site.

It is the Coordinating Investigator's (CI's) responsibility to supervise the general conduct (e.g. Study progress, communication, protocol training and support of the participating sites, annual reporting to the Ethics Committee (EC), end of Study notification(s) and results reporting...) of the Study. The CI fulfils both Investigator and Sponsor responsibilities, as outlined in International Conference on Harmonisation – Good Clinical Practice (ICH-GCP) E6(R2) and applicable regulations.

PI and CI shall each be referred to as «Investigator(s)».

## STUDY SYNOPSIS

Title of clinical Study («Study»)	Efficacy and safety evaluation of MONOBLUE DUAL View and MONOBLUE ILM View vital stains during vitrectomy surgery
Protocol Short Title Acronym	NewBlueDyes
Sponsor name	University Hospitals Leuven (UZ Leuven)>
Principal Investigator	[name]. [name]
Contact Address PI	UZ Leuven, [name]
Contact Email PI	[contact]
Contact Phone PI	[name]
Other public database nbr	NA
Coordinating Investigator	NA
Medical devices	Monoblue Dual View Monoblue ILM View
Study rationale	Retrospective Data Collection
Primary objective	Efficacy: visualization of membranes stained based on binary subjective evaluation.
Secondary objective(s)	

• Efficacy: subjective assessment of surgical help provided by the product

• Safety:

○ Rate and severity of potential study-related products adverse events

○ Visual outcome at the last postoperative visit

Endpoints	Effectiveness Outcomes: Improvement in BCVA after 2 months as compared to preoperative BVCVA. Safety Outcomes: Safety will be assessed based on incidence and severity of investigational device-related adverse events.
Time frame of collecting data for retrospective analysis	SEPTEMBER 2021-APRIL 2022

## I Background and Rationale

Retinal surgery was first performed in the 1960-ies when Charles Schepens developed the technique of scleral buckling using indirect ophthalmoscopy. Later on, pars plana vitrectomy was developed by pioneering surgeons such as Robert Machemer and Relja Zivojinovic. The latter surgical technique became widely adopted in the 1980-ies.

During vitrectomy surgery, there is often the need to remove tissue from the neural retina:

- Epiretinal membranes (ERM): newly formed tissue from dedifferentiated retinal pigment epithelial (RPE) cells. These membranes typically are observed in the following diseases:
  - Macular pucker: formation of fibrosis over the macula, most frequently seen after the formation of posterior vitreous detachment.
  - Proliferative vitreoretinopathy (PVR): formation of fibrotic scars mostly in the (mid)periphery of the retina, most frequently seen in long-standing retinal detachment and after previous retinal surgery.
- Inner Limiting Membrane (ILM): the most inner layer of the retina, formed by the basal membranes of the Müller cells. The removal of this ILM is required to treat different diseases of the retina:
  - Macular hole
  - Vitreomacular traction
  - Macular edema
  - Also, in case of surgery for removal of macular pucker or PVR, concomitant removal of the ILM is frequently performed to avoid re-growth of these membranes.

ERM and ILM are both transparent tissues, similar to the neural retina. Hence, it is not that easy to remove ERM and ILM without touching (and damaging) the underlying neural retina. For this purpose, vital dyes have been developed to selectively stain the tissues that need be removed without staining the underlying neural retina.

The first dye used (off-label) to stain the ILM was Indocyanine Green (ICG), but several reports of toxicity after using that dye have been published. Hence, its use is nowadays mostly abandoned.

Shortly thereafter, Trypan Blue (TB) was introduced to stain ERM. Till today, this dye is used on-label and available from different manufacturers. TB is commercialized in a 0.06% concentration to stain the lens capsule and in a 0.15% concentration to stain ERM. Although TB has good staining properties of ERM, it induces only minimal staining of the ILM.

A few years later, Brilliant Blue G (BBG) was commercialized to selectively stain ILM, and is today still the golden standard for ILM staining. BBG offers a good and selective staining of the ILM, and is a rather transparent solution, hence the surgeon can see the surface of the retina during the surgery. However, BBG hardly stains the ERM.

The first commercial TB and BBG vital dyes were dissolved in BSS, hence had the same gravity as the BSS used to infuse the eye during vitrectomy surgery. As a result, when injecting a 'cloud' of the vital dye, it was difficult for the dye to reach and color specifically the desired retinal tissue. In newer commercial products, the dyes are dissolved in a heavier-than-water dissolvent (such as poly-ethylene glycol: PEG), which makes them sink down to the retinal surface when injected in the vitreous cavity during surgery.

Since it is frequently necessary to remove both ILM and ERM during vitrectomy surgery, solutions that combine TB and BBG are now also available.

In UZLeuven, two types of vital stains are being used during vitrectomy surgery:

- BBG 0,025 % dissolved in PEG (ILM Blue® – DORC): when only ILM peeling is required.
- BBG 0,025 % + TB 0.15% dissolved in PEG (Membrane Blue Dual® – DORC): when either ERM removal is required, or combination of ERM + ILM removal.

More recently, two new staining dyes were commercialized by ARCADOPHTA:

- Monoblue ILM View: DDG 0.025 % dissolved in PBS (phosphate buffer saline) with 2.6% diglycerol. DDG is a triphenylmethane dye with a chemical formula:  $C_{46}H_{46}N_3NaO_7S_2$  and a molecular weight of 840 Dalton. This dye is used to stain the ILM, similar as ILM Blue. The diglycerol makes it heavier than water to optimize the contact between the dye and the retina, similar as ILM Blue.
- Monoblue Dual View: DDG 0.025 % and Trypan Blue 0.09% dissolved in PBS with 2.6% diglycerol, which is used the same way as Membrane Blue Dual.

In laboratory and ex vivo tests, it was shown that both dyes have the following properties:

- Monoblue ILM view:
  - It stains ILM as good as ILM Blue.
  - It is heavier than water, hence sinks down to the retinal surface.

#### Monoblue Dual View

- Monoblue Dual View may offer better transparency to see the retinal surface during surgery compared to Membrane Blue Dual.
- It has a lower concentration of TB, but is still expected to stain ERM as effectively as Membrane Blue Dual, but with a potential better safety profile since its lower concentration.

Both above mentioned dye solutions were CE marked on April 22, 2021 by ARCADOPHTA, located [name], known as the legal manufacturer (see to CE certificate and Declaration of Conformity (DC) provided herewith in **Appendix IA, IB, IC**).

We obtained approval from the CMM UZLeuven to perform a demo with these products. For this purpose, samples of Monoblue ILM View and Monoblue Dual View were obtained from the manufacturer.

#### Study products:

This clinical study is a post-marketing clinical follow-up study of two medical devices: Monoblue ILM View and Monoblue Dual View, legally marketed in EU by the company Arcadophta, and to be conducted in accordance to the provisions of the respective IFU (instructions for use) provided in **Appendix 2**.

#### Intended Use:

The products are intended for use as an aid during vitrectomy procedure in adult that will undergo a vitreoretinal surgery.

Monoblue ILM View is indicated for staining of the Internal Limiting Membrane (ILM)

Monoblue Dual View is indicated for staining of ILM and ERM (Epiretinal Membrane).

## Study population

The study population consists of adult patients with retinal conditions requiring peeling of ILM and/or ERM

## Mechanism of action

MONOBLUE-ILM VIEW and MONOBLUE-Dual View are staining solutions for the posterior eye segment. They are intended to be applied directly to the areas of the membranes to be removed and color all parts of the membrane with which they come into contact, without penetrating these membranes.

## 2 Study Objectives and Design

### 2.1 Study objectives

To determine efficacy and safety of MONOBLUE DUAL View and MONOBLUE ILM View (study products) vital stains during vitrectomy surgery

Both study products are CE-marked and legally marketed in Europe. The data collection will serve as Post-Marketing Clinical Follow-up according MDR provisions. Retrospective data will also be collected for the two reference products: ILM Blue® (DORC) and Membrane Blue Dual® (DORC) to serve as control. For this purpose, patient data will be used that were collected in studies S61408 (Comparative study 23G vs 27G vitrectomy), S63610 (Comparative study 27G vitrectomy vs larger gauge surgery) and S64913 (EVA Nexus Field Observation Study).

The expected effect of the study products is to provide the retinal surgeon with adequate aid in visualizing the membranes involved in the retinal pathology to treat, thanks to their staining capabilities. The performance of the study products is related to the visualization of retinal tissues (ILM and/or ERM) during the vitrectomy procedure, when these tissues cannot be distinguished accurately enough without staining. Their use allows for better identification of these tissues and facilitates their removal by the surgeon. The clinical benefit of using ophthalmic dyes is to increase the patient's ability to recover anatomically and functionally by allowing more precise surgery with an effective visualization tool.

Along with collecting post-marketing clinical follow-up data on the subject products, the outcomes of the present study results may be used at the UZLeuven Hospital to decide to use Monoblue ILM View and/or Monoblue Dual View as standard-of-care, replacing Membrane Blue Dual and ILM Blue.

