## 2.4 Time frame of the retrospective analysis

SEPTEMBER 2021 – APRIL 2022

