## 3 Study Population / Eligibility Criteria

### 3.1 Inclusion criteria

Participants eligible for inclusion in this Study must meet **all** of the following criteria:

Adult patients who underwent for vitrectomy surgery where ILM and/or ERM removal is required:

- Macular holes (ILM staining)
- Macular pucker (ILM and ERM staining)
- Vitreomacular traction (ILM staining)

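### Control eyes come only from participants in three other studies, no such entry step is stated for the Monoblue eyes, and the propensity score has no term for source study, period or gauge

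*Combined protocol and SAP*

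**What the plan says.** Section 2.1 names one origin for control data: "For this purpose, patient data will be used that were collected in studies S61408". The full list is "S61408 (Comparative study 23G vs 27G vitrectomy), S63610 (Comparative study 27G vitrectomy vs larger gauge surgery) and S64913 (EVA Nexus Field Observation Study"). No other source of control eyes is given, and the documents do not describe the entry criteria or dates of these studies.

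The Monoblue eyes have a different origin. Section 1, under Monoblue Dual View, reports: "We obtained approval from the CMM UZLeuven to perform a demo with these products". It adds that "samples of Monoblue ILM View and Monoblue Dual View were obtained from the manufacturer". Enrolment of these patients in any of the three source studies is neither stated nor excluded.

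The eligibility rules in section 3 cover everyone ("Participants eligible for inclusion in this Study must meet" all the listed criteria), with no separate rule for control eyes. Section 2.4 gives a single window, "SEPTEMBER 2021 – APRIL 2022", not split by dye.

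Section 1 also says: "In UZLeuven, two types of vital stains are being used during vitrectomy surgery". These are the two control dyes, so eyes treated with them outside the three studies may well exist in the same hospital record. The plan neither uses them nor says why not.

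Section 4 builds one propensity score per dye pair from age, gender, acuity of the affected eye and surgery type (vitrectomy alone or with phaco).

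**The concern.** On the plan's wording, a control eye passes two filters: the section 3 criteria, and entry into one of three studies set up for another purpose. For a Monoblue eye only the first filter is stated. If the second filter is related to how hard a membrane is to stain or peel, or to the risk of complications, part of its effect may show up as an effect of the dye. Two of the source studies were built around gauge, so gauge mix is a particular feature of the control data.

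The stakes follow from the hypothesis in section 2.3, which is non-inferiority on a subjective yes/no outcome. If selection lowers observed success among controls, an inferior dye can pass; if it raises it, an adequate dye can fail. Adverse events and visual outcome are compared with the same controls. Section 2.1 says the results may inform a decision to replace the hospital's standard dyes.

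**Working it through.** The plan gives no margin, success rate, sample size or power, so there is no figure of its own to reproduce. The check is a comparison of passages, followed by two illustrations on assumed inputs.

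**1. Route into the dataset**

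| | Control eyes | Monoblue eyes |
|---|---|---|
| Origin | Three earlier studies (2.1) | Demonstration with manufacturer samples (1) |
| Section 3 criteria | Apply | Apply |
| Further entry step | Participation in a source study | None stated |
| Dates | Not given for the source studies | After "CE marked on April 22, 2021"; window in 2.4 |
| Gauge | A design factor in two of three sources | Not stated |

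**2. What the window covers.** Section 2.4 can be read as limiting operations in both dye groups, as limiting Monoblue operations only, or, following the synopsis label, as the months in which data are gathered. Under the first reading period is aligned. Under the others it may not be. The text does not settle which is meant.

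**3. What the analysis can remove.** The score and the outcome regression use the same four covariates. Double robustness protects against misspecifying one of those two models; it does not protect against a factor absent from both. Balance checks on the four covariates cannot reveal an imbalance in source, period or gauge. Section 4's statement that the procedure gives an unbiased effect therefore depends on there being no such factor.

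**4. Illustrative size of bias (all inputs assumed).** Bias in the success difference = difference in prevalence of a selection factor × its effect on success.
- Low: 0.20 × 0.10 = 0.02, or 2 points.
- High: 0.40 × 0.20 = 0.08, or 8 points.

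**5. Illustrative consequence for non-inferiority (all inputs assumed).** Sample size per arm at one-sided 2.5%, 80% power and equal true rates: n = (1.960 + 0.842)² × 2p(1 − p)/m². For p = 0.90 and m = 0.10 this is 7.849 × 0.18/0.01 = 141.3, so 142.

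Now let the new dye be truly worse by exactly the margin, and let selection lower observed control success by b. The chance of a false non-inferiority claim is Φ(b/SE − 1.960), with SE² = [(p − b)(1 − p + b) + (p − m)(1 − p + m)]/n. For p = 0.90, m = 0.10, b = 0.03: SE = √[(0.1131 + 0.1600)/142] = 0.0439; 0.03/0.0439 = 0.684; Φ(−1.276) = 0.101.

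| Control success | Margin | n per arm | b = 0 | b = 3 points | b = 5 points |
|---|---|---|---|---|---|
| 90% | 10 points | 142 | 2.5% | 10.1% | 19.8% |
| 95% | 10 points | 75 | 2.5% | 8.4% | 15.1% |
| 90% | 5 points | 566 | 2.5% | 30.7% | 65.4% |
| 95% | 5 points | 299 | 2.5% | 24.9% | 53.1% |

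This is a normal approximation that ignores weighting. It shows how sensitive a non-inferiority claim is to a few points of bias, not what the bias in this study is.

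**The case against.** The strongest reply is that the two groups share more than they differ. The same section 3 criteria apply to all eyes, covering indication, concomitant eye disease and attendance at the 6 to 10 week visit. Comparisons are made within dye pair, which partly separates ILM-only surgery from ERM surgery. The source studies may have had broad criteria, close to section 3. All of this stands: the issue is an added filter on a shared population, and its effect could be small.

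A reader might infer that calendar period definitely differs. The documents do not support that. No source-study dates are given, and the single window, read literally, would bind control eyes too.

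A reader might also infer that the Monoblue eyes were certainly outside the three studies. That is an inference from silence; overlap is not excluded.

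Finally, it is tempting to require concurrent routine eyes as the primary control. That would not clearly be less biased. In a demonstration, the eyes given the new dye may have been chosen by case, which would leave the unchosen ones as concurrent controls. Nor do the documents establish that routine reports answer the specific staining questions in section 5.2.

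None of this answers the central point: source study, period and gauge are not adjusted for, and the plan does not show that they are balanced.

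**Conclusion.** The point holds as a possible, unadjusted difference in selection between dyes. Control eyes carry a stated extra entry step, no such step is stated for Monoblue eyes, and neither the propensity score nor the outcome model can correct for it. Calendar period may differ as well, because the reach of the window is unstated.

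Size and direction cannot be derived from the documents. The 2 to 8 points and the false-claim rates in the table rest wholly on assumed prevalences, effects, success rates and margins, and the table also assumes that the bias acts against control. They should not be cited as estimates for this study. The change is worth making because it is cheap and would expose a bias that the planned analysis cannot show.

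**What to change.** (a) Before any outcome is extracted:
- State which calendar window applies to each dye group.
- Apply the recorded clinical eligibility criteria of S61408, S63610 and S64913 to the Monoblue eyes compared with controls from that study, and write down how the three sets combine in the pooled analysis. Consent to take part cannot be replicated; say so as a limitation.
- Show the flow of eyes by source study and dye.

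Adding source study to the score would not do the same job: if Monoblue eyes belong to none of the three studies, there is no overlap to weight on. The harmonisation has to be made at selection.

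(b) Keep the three-study controls as primary, and prespecify two sets of sensitivity analyses:
- leave out each source study in turn;
- use all eligible ILM Blue and Membrane Blue Dual eyes operated in the Monoblue period, where the surgical report answers the staining questions in section 5.2. Note in the plan that these concurrent eyes may carry their own selection by case.

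The cost is protocol wording, the loss of some Monoblue eyes under (a), and extra chart extraction from the same record system under (b).

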### 2.3 Secondary Endpoints

- Efficacy: subjective assessment of surgical help provided by the product
- Safety:
  - Rate and severity of potential study-related products adverse events
  - Visual outcome at the last postoperative visit

The study hypothesis to be verified is non-inferiority in term of efficacy between study products and comparator based on a binary subjective evaluation of visualization of membranes stained. The proportion of success between study products and comparator will be studied, covariates (age, gender, visual acuity in the affected eye, surgery type being vitrectomy or phaco plus vitrectomy) taken into using a propensity score methodology.

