## 4 Statistics and Data Analysis

The primary outcome of the study is the success of the products based on assessment of efficacy of the staining dye.

Safety of the dye will be assessed by comparing the surgical outcome of the patients to a similar control group that underwent surgery using the staining dyes presently used in our department (see study endpoints).

Statistical analyses will be performed with R version 3.6.2 or higher. In case of missing values, the underlying missingness process (MCAR, MAR or MNAR) will be investigated and 15 multiple imputations will be performed using the **MICE** R package.

We will test with the statistical test of Jamshidian and Jalal (2010), implemented in the **MissMech** R Package (Jamshidian, Jalal & Jansen, 2014), whether missing data were MCAR. If they were not MCAR, we investigated whether or not the missing mechanism could be explained by baseline characteristics (eg, sociodemographic, medical features) of patients using logistic regression, which would suggest an MAR mechanism. If missing data were not MCAR or MAR, they were considered as MNAR.

For each dataset created, two propensity scores will be performed: a first one between the Monoblue ILM View and the ILM Blue, and a second one between the Monoblue Dual View and Membrane Blue Dual. The next covariates were selected for the propensity score: age, gender, visual acuity of the affected eye, surgery type of the affected eye (vitrectomy only vs phaco and vitrectomy). The Covariate Balancing Propensity Score provided in the R **CBPS** package (Imai & Ratkovic, 2014) will be used to estimate an Average Treatment Effect (ATE). The ATE will be estimated by covariate balancing and requesting an exact match. An absolute standardized difference less than 10–15% will be considered to support the assumption of balance between the groups. Unlike the P-value, this method is not affected by the sample size, and it could be used to compare the relative balance of variables that were measured in different units (Austin, 2011). Results (obtained after matching) will be expressed as the mean and standard deviation (SD) for continuous variables or the percentage for categorical variables. The **survey** R package will be used to perform linear regressions for continuous outcome variables and logistic regressions for binary variable. These regressions

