will include the treatment group effect, the weight resulting from the matching, and variables present in the propensity score. This procedure will provide a doubly-robust estimator, which corrected the last remaining possible imbalance between the covariates and produced an unbiased treatment effect (Funk et al., 2010). We will then combine results of the 15 regressions by taking the mean of the estimates of the regression coefficients of the treatment effect and the its associated p-value for each imputed dataset (the so-called, 'Mite approach'), as described by Leyrat et al. (2019). Adjusted P-values less than 0.05 will be considered significant.

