**Secondary endpoint: assessment of surgical safety**

The following endpoints will be used to determine surgical safety:

- Occurrence of adverse events during or after the surgery, whereby both treatment groups will be compared to the corresponding control groups (see above). Occurrence of adverse events will be collected over the duration of the study and up to week 6-10 postoperative, and will be assessed cumulatively.
- Visual outcome at the last postoperative visit, i.e. week 6-10 after the surgery

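### Two of the three control sources are titled as gauge comparisons, but no analysis balances, adjusts for or checks gauge, so a gauge difference could pass for a dye effect on safety and vision

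*Combined protocol and SAP*

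**What the plan says.** **Where the groups come from.** Section 2.1 draws the ILM Blue and Membrane Blue Dual controls from three earlier studies: "S61408 (Comparative study 23G vs 27G vitrectomy), S63610 (Comparative study 27G vitrectomy vs larger gauge surgery) and S64913 (EVA Nexus Field Observation Study". The Monoblue products reached the hospital as manufacturer samples (Section 1, under Monoblue Dual View): "We obtained approval from the CMM UZLeuven to perform a demo with these products". The protocol does not state the gauge used in those operations.

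**What is balanced.** Section 4: "The next covariates were selected for the propensity score: age, gender, visual acuity of the affected eye, surgery type of the affected eye". Surgery type here means phaco or no phaco. Section 4 defines it that way, and so does Section 2.3: "covariates (age, gender, visual acuity in the affected eye, surgery type being vitrectomy or phaco plus vitrectomy".

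**What is adjusted for.** The outcome regressions in Section 4 "will include the treatment group effect, the weight resulting from the matching, and variables present in the propensity score".

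**What is compared.** Section 4: "Safety of the dye will be assessed by comparing the surgical outcome of the patients to a similar control group". Section 5.2 makes the adverse event comparison explicit: "Occurrence of adverse events during or after the surgery, whereby both treatment groups will be compared to the corresponding control groups". It also lists visual outcome at the week 6-10 visit.

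**What is restricted.** Sections 3.1 and 3.2 select on age, indication, concomitant eye disease and attendance at the postoperative visit. They do not select on gauge.

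**The concern.** Adverse events and vision some weeks after a vitrectomy reflect the whole operation, not the dye alone. If the control eyes and the Monoblue eyes were operated on with different mixes of gauge, and if gauge affects these outcomes, part of the difference between dye groups belongs to the instruments.

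Gauge deserves attention here, more than other unlisted surgical details, because two of the three control sources identify themselves by it. Patients in a study that compares gauges need not have the gauge mix of patients treated during a product demonstration. The plan calls the control group similar but does not examine it on this feature.

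The bias could go either way, creating an apparent safety signal or hiding a real one. Section 2.1 says the results may inform whether the hospital replaces its present dyes, so the safety comparison has a practical use beyond description.

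**Working it through.** The plan states no sample size, event rate, margin or gauge mix, so it has no figure to reproduce. The check is whether any step of the plan handles gauge, followed by an illustration of size in which every input is assumed.

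**Step 1. Follow gauge through the plan.**

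| Step | Variables used | Gauge? |
|---|---|---|
| Eligibility (3.1, 3.2) | age, indication, concomitant eye disease, follow-up visit | no |
| Propensity scores (2.3, 4) | age, gender, visual acuity, phaco or no phaco | no |
| Outcome regressions (4) | dye group, weight, the same four variables | no |
| Standardized-difference check, limit 10-15% (4) | read as the propensity score variables | no |
| Listed endpoint items (5.2) | staining answers, adverse events, vision | no |

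The last row does not show that gauge goes unrecorded. Age and gender are not in that list either, and the plan uses both.

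**Step 2. Does the doubly robust estimator cover it?** Double robustness protects when one of the two models, propensity or outcome, is wrong and the other is right. Here both omit the same variable. If gauge is a confounder, neither model is right, and the unbiasedness claimed in Section 4 does not extend to it. All four listed covariates could meet the 10-15% limit while gauge does not.

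**Step 3. Form of the bias.** Suppose the outcome depends on dye and gauge additively. Leaving gauge out gives approximately

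spurious dye difference = (difference between dye groups in the share of one gauge, after weighting) × (effect of that gauge on the outcome).

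If either factor is zero, the product is zero.

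**Step 4. Size in the adverse event rate (both factors assumed).**

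| Imbalance in gauge share | Gauge effect 0 points | 5 points | 10 points |
|---|---|---|---|
| 0 points | 0 | 0 | 0 |
| 25 points | 0 | 0.25 × 5 = 1.25 | 0.25 × 10 = 2.5 |
| 40 points | 0 | 0.40 × 5 = 2 | 0.40 × 10 = 4 |

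The range is 0 to 4 points.

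**Step 5. What a bias of this order does to a test.** Take the 25-point row, with an assumed control rate of 10%, assumed group sizes and no true dye effect.

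- Adverse events: the chance of a significant result in the direction of the bias, at two-sided 0.05, is 3.9% to 5.9% with 50 eyes per group, 4.7% to 8.1% with 100 and 6.0% to 12.1% with 200. The nominal value in that direction is 2.5%.
- Vision: with an assumed SD of 0.30 logMAR and a gauge effect of 0.05 to 0.10 logMAR, the spurious difference is 0.25 × 0.05 = 0.0125 to 0.25 × 0.10 = 0.025 logMAR. The two-sided false-positive rate is 5.5% to 7.0% with 50 per group, 6.0% to 9.1% with 100 and 7.0% to 13.3% with 200, against 5%.

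A larger sample does not remove the bias. It makes a false finding more likely.

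**The case against.** The strongest reply is that nothing shows confounding here. It requires both an imbalance and a gauge effect, and the documents supply neither. Only patients in the earlier studies who received a reference dye and meet Sections 3.1 and 3.2 can serve as controls, and the gauge mix of that subset is unknown. A study title shows that a question was asked, not that an effect exists. All of this stands, and it limits the point to a possible bias.

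The affected outcomes are also secondary: the stated hypothesis in Section 2.3 is non-inferiority of staining visualization. The synopsis and Section 2.3 speak of device- or product-related adverse events, so attribution might filter out some gauge-related events. That helps only partly. Section 5.2 compares adverse events during or after surgery more broadly, and vision passes through no such filter.

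A reader might go further in four ways that the documents do not support:

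- **Machine as a second established confounder.** The title of S64913 might suggest that those controls are tied to a particular surgical machine. The protocol gives only the title and does not describe the device or the study.
- **Gauge known to matter.** One might infer that the sponsor ran the two gauge studies because gauge changes results. Section 2.1 gives codes and short titles, with no sponsor, objective or result.
- **A known gauge in the Monoblue eyes.** None is stated, nor is it said that they used whatever was then current.
- **A failed balance check.** An assumed 27G share of 50% in controls and 90% in Monoblue eyes would give a standardized difference of 0.40 / √((0.50 × 0.50 + 0.90 × 0.10) / 2) = 0.40 / 0.412 = 0.97, far above 0.10-0.15. The split is invented for the example, so the figure says nothing about the actual groups.

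**Conclusion.** The point holds for gauge, as a gap in the plan and not as a demonstrated bias. Two of the three control sources are titled as gauge comparisons, no step of the analysis uses gauge, and the doubly robust estimator cannot repair a variable missing from both of its models. The comparison of adverse events and week 6-10 vision is therefore open to a gauge difference that the planned check would not reveal.

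The size cannot be known from the documents. On the assumed ranges (imbalance of 0 to 40 points, gauge effect of 0 to 10 points, additive effects), the spurious difference in adverse event rate lies between 0 and 4 points, in either direction. It is zero if the weighted groups have the same gauge mix or if gauge does not affect the outcome. The claim does not extend to the surgical machine, about which the documents say too little. This is a cheap improvement worth making before the analysis, not a flaw that invalidates the comparison.

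**What to change.** 1. Extract gauge and source study for every eye from the surgical reports and study records, and report both by dye group, separately for the ILM and the dual comparison.
2. Where both dye groups share gauges, add gauge to both propensity scores, to the outcome regressions and to the standardized-difference check.
3. Add a sensitivity analysis of adverse events and vision restricted to gauges present in both dye groups. Keep it as a sensitivity analysis, not a condition of the main one. Where a gauge occurs in only one group, adjustment cannot separate it from the dye, and this analysis is where that would show.
4. If the records show that the surgical machine differs between groups, tabulate it in the same way.

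**Cost.** Surgical reports are already read for the staining answers, so the work is one or two extra fields and one extra covariate. The drawback is some loss of effective sample size if gauge is strongly imbalanced. That deserves care: the plan states no sample size, asks for an exact match and splits the data into two dye comparisons, so the restricted analysis could be small. If gauge proves balanced, one added table row per comparison documents it.
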